9.2.8. Venipuncture for IgE

Approximately 5 cc of blood will be obtained by venipuncture (and no more than 3 cc/kg body weight) and after preparing the skin with a local anesthetic, per participant preference. Within one hour of collection, the specimen is centrifuged and serum and plasma aliquoted, with removal and storage of the buffy coat if applicable. Following instructions outlined in the Laboratory MOP, the specimen is stored locally at -80°C and shipped on dry ice in batches as per the MOP to the central laboratory at Children's Hospital of Philadelphia Clinical and Translational Research Center. This sample does not require fasting and may be collected at another time point within 30 days of the baseline visit, per participant preference.

9.2.9. Medical status

The Research Coordinator will obtain baseline information regarding health status and medication according to a standardized script, and enter responses into the CRF.

9.2.10. Sleep educational material is reviewed.

9.3. Randomization

Participants meeting all eligibility criteria will be randomized at the end of the Baseline Visit to either the eAT group or to WWSC. The unblinded coordinator will complete this step in a customized electronic data capture (EDC) system using a standard internet

connection that communicates with the secure study portal. After entering key fields (e.g., stratification variables) and submitting the web-based forms, eligibility will be electronically ascertained. Upon confirmation, the site staff will be presented with the randomization assignment for that participant.

The randomization schema will be setup per the DCC protocol and stored/maintained by the Brigham and Women's Hospital Program in Sleep Medicine Epidemiology. The randomization distributions and system will be re-assessed on a quarterly basis to ensure that it is working as expected. To minimize problems with connectivity, staff will be asked to confirm internet connectivity and EDC system availability at the beginning of the baseline visit to avoid any potential problems accessing the randomization module. If problems arise with connectivity during a given baseline visit, site staff will be asked to immediately contact the Brigham and Women's Hospital Program in Sleep Medicine Epidemiology to resolve these; a manually generated randomization assignment would then be generated based upon the subject criteria. The DCC will be responsible for providing and documenting appropriate user access to the database, preventing against unauthorized entry into the randomization system.

Participants will be assigned randomly to either eAT or WWSC. For those participants assigned to the eAT arm, arrangements will be made by the unblinded coordinator to schedule surgery within 4 weeks of randomization.

9.4. Teacher report forms

BRIEF2/P, Conners 3 Short Form and Teacher Report Form (teacher version of the CBCL) will be mailed to pre-school and schoolteachers. The teacher (or for summer months, the teacher from the preceding semester) will be mailed the forms along with a background letter on the study, written permission to contact them signed by the parent and a gift card as an incentive. Repeat mailings, and if needed phone calls, will be made if forms are not returned within 2 weeks. At each subsequent visit, caregivers will also be asked to bring in the child's most recent report card so that school absences and grades can be recorded and used for exploratory analyses. The teacher ratings will be obtained at baseline, Month 6 and Month 12. Permission to contact the child's primary or homeroom teacher will be obtained from parents at the time of consent, and again at the time each follow-up visit is scheduled.

9.5. Monthly caregiver interviews

As part of ongoing contact with participants (see Appendix A Visit Schedule), caregivers will be contacted on a bi-monthly basis for completion of check in questionnaires and surveys. Centrally trained research coordinators will administer these questionnaires by telephone, email and/or text messaging at months 2, 4, 6, 8, 10 and in person visit at 12 months. A structured interview that will identify adverse events and HCU, including hospitalizations (reason, place and number of days), emergency room visits (reason, place), unscheduled and scheduled medical outpatient visits, and medication prescriptions. The coordinator will use a script with follow-up questions and record all information in the CRF.

If parents cannot be reached by phone for monthly calls, we will provide parents direct links to The SLICE data management system provided by The DCC. However, adverse

events and healthcare utilization will be followed up by phone calls as there are many nuances that need direct communication with the coordinators.

On alternate months of check in questionnaires, caregivers will be contacted to assess for adverse events and health care utilization only.

9.6. Health care utilization (HCU) and electronic medical record (EMR) surveillance

EMR will be tracked by both monthly manual review of EMR by the Research Coordinator after each reported adverse event or HCU event, and by automated surveillance of billing records and pharmacy records using query systems co-developed by [name], conducted approximately bi-annually. At each monthly check-in by telephone, email and/or text messaging, or in-person visit, the research coordinator will conduct a structured interview that will identify adverse events and HCU, including hospitalizations (reason, place and number of days), emergency room visits (reason, place), unscheduled and scheduled medical outpatient visits, and medication prescriptions. Data will be entered into a CRF. In addition, each health system's billing system informatics analytics team will extract relevant information from inpatient, outpatient and pharmacy records as outlined in the DCC application. Query results will be returned monthly to the research coordinator who will extract the information to the CRF and compare these data to the parent-reported data. When discrepancies are identified, the research coordinator will attempt to resolve differences by further interviews with the caregiver, requests to other health institutions for medical record release, or by consulting with the DCC. Healthcare utilization data will be collected prospectively through ongoing surveillance of electronic medical records (EMR) for up 24 months following randomization of subjects. We will utilize a query structure to be used by the EMR informatics analytics team for ongoing EMR surveillance for extracting relevant information from inpatient, outpatient and pharmacy records.

9.7. Study Visits (see Appendix A for Summary of Visit Schedule and Procedures)

The details of the specific study procedures at each study visit are summarized in the previous section. This section lists the study visits and summarizes the procedures at each visit.

9.7.1. Screening visit/PSG eligibility – Day -60 to -1

At this visit, preliminary study eligibility is confirmed and informed consent obtained. If the participant had a clinical PSG, then these data are sent to the DCC/ Reading Center to confirm eligibility. If the participant has not had a PSG, then a research PSG is performed.

9.7.2. Baseline visit – Day 0

After PSG eligibility for MSDB is confirmed, this visit includes anthropometry, BP measurement and physical examination. The child completes behavioral performance measures and the parent completes questionnaires about behavior & attention, SDB symptoms, sleepiness, quality of life and family functioning. Children \geq 5 years of age also complete the child version of the PedsQL. Urine is collected for cotinine and serum

IgE is collected by venipuncture. The research coordinator inquiries about adverse events, changes in health status or medication, and HCU. Eligibility is confirmed and the participant is randomized. Behavioral rating scales are mailed to teachers.

9.7.3. Monthly Check-In – Months 1, 2, 3, 4, 5, 7, 8, 9, 10, 11

Between each face-to-face visit, study staff will make contact by telephone, email and/or text messaging, with families in both groups for inquiries about adverse events, medications, and changes in health status using a study CRF. HCU is assessed and EMR surveillance completed. Participants are reminded about upcoming study visits and study participation is reinforced.

9.7.4. Remote Interim Visit – Month 6

The parent completes questionnaires about behavior, SDB symptoms, sleepiness, quality of life and family functioning. Study staff inquire about adverse events, changes in health status or medication, and HCU. EMR surveillance is completed. Behavioral rating scales are mailed to teachers. Note that with the Covid-19 pandemic, 6 month visits can be held virtually if in-person visits are not possible, focusing on parent-related questionnaires.

9.7.5. Endpoint PSG – Month 12

Participant completes overnight PSG using the same protocol as for baseline PSG.

9.7.6. Endpoint daytime visit – Month 12

This visit includes measurement of anthropometry, BP and behavioral performance testing. Parent completes questionnaires about behavior and attention, SDB symptoms, sleepiness, quality of life and family functioning. Participants \geq 5 years also complete the child version of the PedsQL. Study staff inquire about adverse events, changes in health status or medication, and HCU. Behavioral rating scales are mailed to teachers. Participants in the WWSCL arm are scheduled for re-evaluation with their ENT surgeon within 1-4 weeks if indicated.

9.7.1. Post-participation Surveys

The research coordinator will ask and verbally consent all participants to complete 3 follow up questionnaires after completion of the study via email, mail or phone.

9.8. Potential Treatment Failures

During the trial, the research coordinator may discover signs and/or symptoms that could potentially indicate treatment failure regardless of the arm assignment. “Treatment failure” is generally defined as a condition or situation that is observed during either routine interim follow-up phone calls or any study visits or clinical visits discovered in EMR surveillance, or from parent or physician contact, and indicates a potential need to change treatment. See Adverse Events section.

The research coordinator has the responsibility to:

- Identify and record these events utilizing the Treatment Stop [TSTOP] case report form (at this stage they are “potential” Treatment Failures).
- The research coordinator will notify the PI, who will make any decisions required for the participant’s clinical safety. The study team will make appropriate arrangements for further follow-up/referral (e.g., back to the referring physician).
- Follow the general procedures for reporting SAEs (i.e., notify the DCC Project Manager within 24 hours of first knowledge of the event) and Complete the SAE/Treatment Failure report within 48 hours of first knowledge of the event. It will be submitted to the DCC who will forward the AE report and all supporting documents to the Medical Monitor via the data management system (Slice). Instructions for completing and submitting this information will be listed on the form and details provided in the Master Manual of procedures. Diagnostic information that will assist in the understanding of the event may be requested and follow up reports may be necessary. Significant new information on ongoing serious adverse events should be provided promptly to the DCC.
- The Medical Monitor will determine if the event meets Treatment Failure criteria. This information, including specific reasons for failure including why a physician involved in the child’s care determined alternative therapy and which alternative therapy was recommended, will be documented on the [TSTOP] CRF and entered into the data management system. If there is discordance between the PI and the external Medical Monitor, then the Medical Monitor’s decision will be used for data analytical purposes. All reports of Treatment Failures will be tabulated as aggregate data and summarized monthly for review by the Steering Committee (in blinded format) and quarterly to the DSMB (or more frequently based on the trends and the Steering Committee’s recommendations).

9.9. Adverse Event Definitions and Reports

9.9.1. Overview of Surveillance for Adverse Events and Safety Indices

Adverse events are monitored through several means of surveillance, as described below:

1. Families will be in contact with study staff monthly by either electronic media (telephone, email and/or text messaging) or face-to-face visits to ascertain if a new medical or behavioral condition requiring therapy or causing interference with daily activities has occurred or been diagnosed, or if any emergency room visit or hospitalization has occurred. EMR surveillance is also used to support these efforts.
2. At each visit (day 0, months 6, and 12), and during monthly check-in, data will be collected that includes changes in health status, medications, SDB symptoms including sleepiness. Also, height, weight and blood pressure data are collected during the in-person visits and can alert study staff to the need for further investigation if problem changes are discovered.
3. Surgical adverse events will be captured by an intraoperative CRF completed by the surgeon and by questionnaires completed via a telephone interview post-operatively, and by ongoing monthly contact and EMR surveillance. Refer to the Surgical MOP for details.

4. Research data will be interrogated to identify questionnaire data exceeding values that indicate an abnormality warranting further investigation.
5. All treatment failures will be reviewed by the study's Medical Safety Monitor in real time and reported to the DSMB on a quarterly basis

9.9.2. Urgent Medical Referral Criteria

Conditions that will generate an Urgent Medical Referral Alert are those laboratory, physiological or behavioral findings that are believed to represent conditions that may require additional evaluation by the participant's health care providers in a timely manner. Because the participants in this study are pre-screened to be "otherwise healthy" children, most participants who meet Urgent Medical Referral Criteria are likely to be encountered at the time of their screening PSG and will no longer be eligible to participate and will exit the study to routine or urgent health care, as appropriate.

NOTE: At the baseline visit, one of the behavioral questions asks about suicidal ideation. A positive endorsement of that symptom will lead the study team to prompt assessment, deferred participation and possibly exclusion from the study, as appropriate for the participant's welfare. CBCL for children 6 years and older, the only measure that assesses for suicidal ideation, will be completed during an in person visit by the blinded RC only.

If the following conditions are identified during the course of the study, their occurrence will generate an Urgent Medical Referral by the Site PI who will communicate with the participant's parent or guardian, and with permission, contact the child's health care provider. Some of these conditions (abnormalities of blood pressure) will be noted as usually needing confirmation with repeat testing before clinical decision making.

- Stage 2 hypertension (> 99% for age and gender)
- PSG: Desaturation to < 90% for > 2% of total sleep time OAI >20/hr. or AHI > 30/hr.
- ABAS-3 score of <60
- Suicidal ideation

It should be noted that if any of these conditions occur after enrollment (i.e., not during a screening visit that disqualifies the child from enrolling in the study), these conditions will also be reported as Adverse Events.

An *Urgent Medical Referral Alert* should be completed and the site PI notified within 24 hours of first knowledge of the event.

9.9.3. Definitions

9.9.3.1. Pre-existing condition

A preexisting condition is one that is present at the start of the study. A preexisting condition should be recorded as an adverse event if the frequency,

intensity, or the character of the condition worsens during the study period. At screening, any clinically significant abnormality should be recorded as a preexisting condition. At the end of the study, any new clinically significant findings or abnormalities that meet the definition of an adverse event must also be recorded and documented as an adverse event.

9.9.3.2. Adverse Event (AE)

An AE is any unfavorable and unintended sign (including an abnormal laboratory finding), symptom, or disease that occurs during a participant's enrollment period in the study including the clinically significant worsening of an already existing symptom, physical sign and abnormal laboratory value, whether or not the event is considered to be related to the study or the intervention under investigation.

Preexisting diseases or conditions present or detected at the start of a study that do not worsen including any day-to-day fluctuations or anticipated day-to-day fluctuations will not be captured as Adverse Events (AE), including those identified as expected to occur in high frequency.

9.9.3.3. Expected (Anticipated) Adverse Event

Adverse events that are expected and are identified in the protocol and for the purpose of this study have been identified as:

- Foreseeable (expected) mild adverse events that may not warrant reporting
- Foreseeable (expected) adverse events that exceed threshold definitions and warrant reporting

The Office of Human Research Protection distinguishes between risks and discomforts that are related to research compared to clinical intervention and have defined new reporting guidelines as of January 17, 2007.

Since the surgical procedure (AT) is being performed as part of usual clinical care (e.g., it is not paid for as a study procedure and is performed as part of routine clinical care), all foreseeable mild AEs that are expected to occur at high frequencies as part of routine clinical care (like PSG or phlebotomy) including those associated with surgery (AT) that do not exceed threshold definitions will not be considered adverse events and will not warrant reporting, such as the following:

Associated with PSG

- Skin irritation from removal of adhesives (lasting < 2 days)
- Temporary depigmentation under area of sensor attachment (lasting < 1 month)
- Poor sleep during PSG

Associated with AT

- Post-op throat pain lasting < 21 days and not requiring intravenous hydration or unscheduled medical evaluation or treatment.

- Post-op hoarseness or difficulty swallowing lasting < 21 days and not requiring intravenous hydration or unscheduled medical evaluation or treatment.
- Intra-operative blood loss <7 ml/kg
- Post-op blood-tinged oral or nasal secretions, lasting < 72 hours
- Velopharyngeal Insufficiency (nasal regurgitation or hypernasality) lasting < 2 months and not requiring specific evaluation or intervention

Associated with Phlebotomy

- Temporary pain, lasting < 48 hours
- Bleeding or bruising at the blood draw site not needing medical attention

Other

- Anxiety surrounding behavioral testing not requiring psychiatric attention and not interfering with completion of the protocol

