9.9.5. Recording and Reporting Adverse Events

At each contact with the subject, the investigator must seek information on AEs by specific questioning and, as appropriate, by examination. Information on all adverse events should be recorded immediately in the source document, and also in the appropriate AE module of the case report form (CRF).

All adverse events occurring during the study period must be recorded. The clinical course of each event should be followed until resolution, stabilization, or until it has been determined that the study treatment or participation is not the cause. The following data will be recorded:

- Any event reported by the participant or parent/legal guardian, other than those expected and identified as detailed in the MOP will be immediately reported to the site PI.
- Signs and symptoms will be graded by the Unblinded Research Coordinator utilizing a 5-grade scale as listed in the manual of procedures.
- Each event will be assessed by the Principal Investigator (PI) for its relationship to study participation according to the guidelines listed in the Manual of Procedures.

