Following 12 months, participants in the WWS group will be referred to ENT for a clinical visit, if their 12-month PSG shows an AHI \geq 3 /hr or obstructive apnea index > 1/hr. or if the parent/caregiver reports concerns or symptoms. The 12-month end point was chosen to enable assessment of long-term therapeutic effects. However, data from the 6-month visit will be used to improve the study's statistical efficiency; help identify the time-course and trajectory of treatment response; and provide information for imputing missing 12-month data. In addition to the efficacy analyses described below, adverse events will be summarized and presented by treatment groups.

Aims, Hypotheses and Endpoints

Aim 1: To determine the effect of eAT on behavior, attention, SDB symptoms, sleep quality, and quality of life in children with MSDB.

Aim 2: To determine the effects of eAT on health care utilization (HCU) in children with MSDB.

Aim 3: To identify factors that moderate the response to AT, including age, asthma/atopy, obesity, secondhand smoke exposure, sleep duration, family functioning socioeconomic status, and race.

Endpoint for Primary Efficacy Hypotheses

The co-primary outcome of the randomized controlled trial will be the GEC Score from the BRIEF2/P and the GNG. Please see the CCC application for details on its reliability, responsiveness, and psychometric properties.

Primary Null Hypothesis

The primary null hypothesis is that the mean change at 12 months in the BRIEF2/P GEC Score and GNG sustained attention d' will be the same for children who were randomized to eAT or to WWS.

Secondary Null Hypotheses

- a) There will be no difference between treatment groups in the expected mean change at 12 months in other behavior/performance measures, SDB symptoms, and quality of life.
- b) There will be no difference between groups in expected HCU (illness or injury requiring hospitalizations; emergency department visits; inpatient procedures; outpatient procedures; scheduled office visits; unscheduled office visits or urgent care visits; medication use) during the 12-month study period.

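### By-arm totals of all or mild adverse events will understate the burden of eAT, because mild post-operative symptoms below set limits are excluded by definition

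*Combined protocol and SAP*

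**What the plan says.** Section 9.9.3.2 defines an adverse event broadly, as "any unfavorable and unintended sign (including an abnormal laboratory finding), symptom, or disease that occurs during a" child's enrollment, whether or not it is related to the study or the intervention. Section 9.9.5 adds: "All adverse events occurring during the study period must be recorded".

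Section 9.9.3.3 then makes an exception. Its reason is that AT is routine care and is not paid for as a study procedure. Foreseeable mild events that "do not exceed threshold definitions will not be considered adverse events and will not warrant reporting" are listed by procedure. The AT list covers:

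- "Post-op throat pain lasting < 21 days and not requiring intravenous hydration or unscheduled medical evaluation or treatment";
- hoarseness or difficulty swallowing, on the same terms;
- intra-operative blood loss under 7 ml/kg;
- blood-tinged oral or nasal secretions for less than 72 hours;
- "Velopharyngeal Insufficiency (nasal regurgitation or hypernasality) lasting < 2 months and not requiring specific evaluation or intervention".

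The same section keeps a second class in the count: "Foreseeable (expected) adverse events that exceed threshold definitions and warrant reporting". It also lists exempt items for polysomnography, phlebotomy and behavioral testing.

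The description of the study in section 19 says that "adverse events will be summarized and presented by treatment groups". It adds no caveat about the exempt events.

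**The concern.** Section 9.9.3.3 takes two decisions in one sentence. One is that these events need no individual report. The other is that they are not adverse events at all. The second sits uneasily with the section's own opening, which describes the same class as mild adverse events that may not need reporting, and with the broad definition in 9.9.3.2.

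The usual-care argument supports the first decision. It does not support the second, because AT is the randomized intervention here. The background section on health care utilization says that a randomized trial is needed to learn whether the benefits of this surgery outweigh its risks, and section 6.1 expects the more intensive arm to carry more risk. Mild post-operative morbidity is part of that balance. Under the present definition it does not reach the by-arm table, nor the adverse-event trends within each arm that the Medical Safety Monitor reviews under section 10.1.

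**Working it through.** The plan states no adverse-event rate, test or power for the by-arm summary, so there is no figure to reproduce. The check is a reading of the definitions, followed by arithmetic on stated assumptions.

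**1. Who is affected.** The exemptions go by procedure, not by arm. Polysomnography, phlebotomy and behavioral testing are scheduled in both arms, so those exemptions are balanced. The AT items can apply only to a child who has AT: nearly always an eAT child, otherwise a WWSC crossover.

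**2. What stays in the count.** Throat pain, hoarseness and swallowing difficulty lose the exemption at 21 days, or with intravenous hydration or unscheduled care. Velopharyngeal insufficiency loses it at 2 months, or with specific evaluation or intervention. Section 9.9.6 makes hospitalization from an adverse event serious. Section 6.2 gives figures from the earlier trial in children with sleep apnea, here scaled to the 230 per arm of section 2.1:

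- emergency department returns: 11/221 = 5.0%; 230 × 11/221 ≈ 11;
- readmissions: 7/221 = 3.2%; 230 × 7/221 ≈ 7;
- returns to the operating room: 2/221 = 0.9%; 230 × 2/221 ≈ 2.

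Events of this kind would still be counted.

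**3. Illustrative size of the omission.** Let b be the background risk of any counted event in 12 months, s = 0.05 the risk of a counted surgical event (from 11/221), and m the risk of at least one exempt post-operative symptom. The ranges b = 0.2–0.6 and m = 0.5–0.95 are assumptions. Independence is assumed, and every eAT child is taken to be operated on.

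- WWSC: b.
- eAT as defined: 1 − (1 − b)(1 − s).
- eAT with exempt symptoms included: 1 − (1 − b)(1 − s)(1 − m).

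| b | m | WWSC | eAT as defined (difference) | eAT, all symptoms (difference) |
|---|---|---|---|---|
| 0.2 | 0.50 | 20% | 24% (+4) | 62% (+42) |
| 0.2 | 0.95 | 20% | 24% (+4) | 96% (+76) |
| 0.6 | 0.50 | 60% | 62% (+2) | 81% (+21) |
| 0.6 | 0.95 | 60% | 62% (+2) | 98% (+38) |

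The number of eAT children with an uncounted event is 230 × 0.5 = 115 to 230 × 0.95 ≈ 219.

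**4. How much the same symptom could be treated differently by arm.** A background sore throat or hoarseness in an eAT child could be absorbed by the exemption only within the 21-day window, which is 21/365 = 5.8% of follow-up. At an assumed r episodes per child-year, the gap is 230 × r × 21/365: about 3 events at r = 0.2 and about 26 at r = 2. This part is small beside the omission in step 3.

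**The case against.** The rule is disclosed, prespecified and confined to mild events. Counting near-universal post-operative pain would dominate an any-event total and hide differences that matter clinically. The section 19 summary is one descriptive sentence with no hypothesis attached. Surveillance is also heavier after surgery: section 9.9.1 gives only operated children an intra-operative form and a post-operative telephone interview, which tends to raise the eAT count. Care-seeking is shown another way, since the Aim 2 analysis of health care utilization is run with and without surgery-related events. Finally, the Surgical Manual of Procedures is not among the documents and may already collect these items.

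Much of this stands. It is a good reason to keep the exempt symptoms out of the main table and to limit the point to totals of all or mild events. It does not remove the point. The utilization analysis cannot show symptoms for which no care was sought. Nothing in the protocol or SAP says that the exempt items are recorded on the surgical forms or presented anywhere by arm. What the manual contains cannot be checked.

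**Conclusion.** The point holds in a limited form. Mild post-operative events below the limits are removed from the adverse-event definition, not only from reporting. They arise almost only after AT, so by-arm totals of all or mild events will understate the burden of eAT. Serious and above-threshold events are unaffected. That direction follows from the definitions; the size cannot be taken from the documents. The 115 to 219 children, and the shift from +2 to +4 points to +21 to +76 points, rest wholly on the assumed b and m.

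A reader might infer more: that the same symptoms count as adverse events in WWSC, so that the comparison is biased in favour of eAT and could show equal or fewer events with surgery. The documents do not support that.

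- No section says that these symptoms count in WWSC. It is an inference from 9.9.3.2 and fits only throat symptoms and perhaps blood-tinged secretions. Intra-operative blood loss needs an operation, and velopharyngeal insufficiency is listed only as a consequence of AT.
- The overlap is confined to a short window and is small (step 4). The monthly inquiry in both arms asks about conditions that needed treatment or disrupted daily life, so a trivial sore throat in WWSC may never be elicited.
- With equal background risk, the illustration still shows 2 to 4 points more events in eAT under the present definition, and the extra surgical surveillance pushes the same way.

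**What to change.** In section 9.9.3.3, keep the exemption from individual reporting, but state that the listed AT items are still recorded (yes/no and duration) on the intra-operative form and the post-operative telephone questionnaire that section 9.9.1, item 3, already requires. In the adverse-event sentence of section 19, state that these items are tabulated separately by arm alongside the main adverse-event table, and that the main table excludes them by definition.

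This needs a few check-box items, if the forms do not already have them, and a short addition to each section. It needs no new visit and no extra expedited reports, and it leaves the thresholds and clinical care as they are. The downside is slightly more data entry and a less favourable harms presentation for eAT.
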